### 14.2 Secondary Efficacy Endpoint Assessment

The primary efficacy endpoint is to assess the clinical response to bisphosphocinTM Nu-3 as determined by visual evaluation of the ulcer following Nu-3 treatment. The measurement of this variable will be determined by the DUSS score at screening, after a single dose treatment (Day 1), after a second dose treatment (Day 2), after twice daily for 7 day treatment, at Day 15.

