#### **Study Design**

Multi center, Randomized Double Blind, Placebo-Controlled, Dose Escalating Study

Clinical investigation Objective(s) and Endpoint:

	Objective	Endpoint	Variable
Primary	To assess the safety and tolerability of escalating doses of topically applied bisphosphocin™ Nu-3	Treatment emergent events related to clinical investigation product	
 
Vital signs,
 
CBC analysis, CMP analysis,
 
Physical examination,
 

Secondary	• To assess the clinical and microbiological response to bisphosphocin™ Nu-3	

Reduction of pathogenic bacteria

Visual evaluation of the ulcer

	

Aerobic and anaerobic culture and sensitivity

DUSS Score

	• To support determination of the appropriate dose range of Nu-3 to be employed in future clinical studies.		

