#### 9.1.1 **Inclusion Criteria**

- 1. Men and women between the ages of 18 and 85.
- 2. Voluntary written consent, given before performance of any clinical investigation-related procedure not part of standard medical care, and with the understanding that consent may be withdrawn at any time without prejudice to future medical care.
- 3. Non-hospitalized ambulatory subjects suffering from Diabetes mellitus, Type I or II
- 4. Diabetic foot ulcer(s) with a DUSS Score of 0 to 3
- 5. Ulcerated area(s) of not more than two (2) ulcers between 0.5 to 6 cm^2
- 6. Any female of child bearing age must consent to use medically acceptable birth control for the duration of the study
- 7. Female subjects must meet at least one of the following additional criteria:
  - d. Surgically sterile with bilateral tubal ligation or hysterectomy.
  - e. Post-menopausal for at least one year.
  - f. If of child-bearing potential, practicing an acceptable method of birth control for the duration of the clinical investigation as judged by the Investigator, such as condoms, foams, jellies, diaphragm, intrauterine device or abstinence.
- 8. Subjects willing to undergo pre-and post-clinical investigation blood collection, physical exams and laboratory investigations..

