#### 9.1.2 Exclusion Criteria

- 1. A DUSS Score above 3.
- 2. DUSS Probing to Bone = "Yes"
- 3. An ulcer area(s) greater than 6 cm^2 or more than two (2) ulcers

- 4. Any subject that has received systemic or topical antibiotics within the last seven (7) days
- 5. Any subject on topical antimicrobial treatment for their infected diabetic foot ulcer whose ulcer is responding to treatment
- 6. Any subject that would be unable to follow the protocol procedures, safely monitor the infection status at home, and return for schedule visits
- 7. Positive pregnancy test at Screening or Visit 2
- 8. Active infection as demonstrated by temperature > 37.5 °C and clinical features of active infection.
- 9. Known immunosuppression or taking immunosuppressive agents including systemic steroids.
- 10. History of severe co-morbidity with expected patient survival  $\leq$  6 months.
- 11. Pregnancy or lactation
- 12. Intake of investigational drugs within 28 days prior to enrollment.
- 13. History of concurrent condition that, in the Investigator's opinion, would jeopardize the safety of the subject or compliance with the protocol.
- 14. Likely inability to comply with the protocol or cooperate fully with the investigator and site personnel.
- 15. Unwillingness or language barrier precluding adequate understanding of the trial procedure or cooperation with trial site personnel.
- 16. Known or suspected active abuse of alcohol, narcotics or non-prescription drugs.
- 17. Other planned surgical procedures within 30 days prior to or 30 days post-index procedure.
- 18. Prior enrolment in this clinical trial

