### 12.2 Visit 1 (Day -7 to -4 hours) - Screening

After granting of informed consent the patient will undergo screening. Screening includes the following:

- Demography data, medical history, general physical examination of all organ systems, and vital signs (blood pressure, heart rate, and temperature): Perform a physical exam and assess vital signs per hospital protocol within the specified timeframe for screening.
- Vital signs measurements: Weight, temperature, resting blood pressure, heart rate, and respiratory rate
- Hematology: WBC, RBC, Hgb, Hct, MCV, MCH, HCHC, RDW, MPV, Platelets, Neutrophils Auto % (abs), Immature Granulocyte Auto % (abs), Lymphocytes Auto % (abs), Monocytes Auto % (abs), Eosinophils Auto % (abs), Basophils Auto % (abs)
- Biochemistry: Sodium, Potassium, Bicarbonate or CO2, Chloride, Total Bilirubin,
   Creatinine, BUN, Calcium, Alkaline Phosphatase, ALT, AST, Total Protein,
   Albumin, Anion Gap, eGFR, Globulin, A/G ration
- For females of child-bearing potential: pregnancy test (urine or serum  $\beta$ -HCG) to be performed at baseline.
- Baseline Patient Disease Assessment: Visual examination of chronic ulcer, score target ulcer using DUSS Scoring System, Swab wound to culture for microbiological examination

Diabetic Ulcer Wound Scoring System (DUSS)

Parameter	Score			
Palpable Pedal Pulses	Presence = 0 Absence = 1			
Probing to Bone	$N_0 = 0$	Yes = 1		
Location of Ulcer	Toe = 0	Foot = 1		
Number of Ulcerations	Single = 0	Multiple = 1		
Score Range	0	4		

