### **Diabetic Foot Ulcer Wound Infection Score**

Parameter	Wound Infection Score			
	0	1	2	3
Purulent discharge	Absent			Present
Nonpurulant drainage (serious, sanguinous)	Absent	Mild		
Erythema	None	Mild pink, barely perceptible	Moderate pale red, defined edges	Severe red to dark red
Induration	None	Mild	Moderate	Severe
Tenderness (sign)	None	Mild	Moderate	Severe
Pain (symptoms)	None	Mild	Moderate	Severe
Local Warmth (relative to uninfected contralateral foot)	Same	Mildly increased	Moderately increased	Severely increased

Photo Documentation and Calculation of the Ulcer Area and Depth using the Aranz Medical SilhouetteTM as described in Appendix A

A past medical/surgical history will be recorded for any conditions or treatments that are, in the opinion of the investigator, relevant to the current diagnosis. The previous condition will be recorded as a diagnosis rather than a previous symptom. The time of the previous diagnosis relative to the current admission will be provided (i.e., "6 months ago") to the best of the patient's knowledge. If the diagnosis was more than two years ago, then it can be recorded as "more than two years ago".

Prior medications will be recorded. Prior medications include medications that the patient is currently taken or has taken within the past fourteen days.

Physical examinations are performed at screening by the investigator or designee. The screening examinations will include general appearance, height, weight, skin, neck, eyes, ears, nose, throat, heart, lungs, abdomen, cervical and axillary lymph nodes, extremities, and nervous system. Height is measured in stocking or bare feet, and recorded in centimeters (cm). Weight is recorded in kilograms (kg).

Results of these investigations/assessments and baseline measurements obtained from the local laboratory will be reviewed by the Investigator prior to the start of the treatment. Patients who do not meet study entry criteria will be promptly notified and excluded from further participation in the study. Patients who continue to meet entry criteria will be enrolled in the study and assigned a patient number by the database. The patient can be randomized at any time following the screening.

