## 16.5 Analysis of Primary Outcome Measure

The microbiological response of Nu-3 to eliminate pathogenic bacteria will be determined for each group. Aerobic and anaerobic culture and sensitivity will be assessed at screening, after a single dose treatment (Day 1), after a second dose treatment (Day 2), after twice daily for 7 day treatment, at Day 15. An uncorrected chi-square analysis or a Fisher's Exact test will be used to compare each treatment group to the placebo group. An associated p-value less than 0.05 will be used to define statistical significance. An associated p-value less than 0.016 ( $0.05 \div 5$ ; Bonferroni correction) will be considered highly conclusive.

The clinical response of Nu-3 via visual evaluation of the ulcer will be determined for each group. DUSS Score will be assessed at screening, after a single dose treatment (Day 1), after a second dose treatment (Day 2), after twice daily for 7 day treatment, and at Day 15. An uncorrected chi-square analysis or a Fisher's Exact test will be used to compare each treatment group to the placebo group. An associated p-value less than 0.05 will be used to define statistical significance. An associated p-value less than 0.016 ( $0.05 \div 5$ ; Bonferroni correction) will be considered highly conclusive.

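### The protocol measures clinical response by DUSS alone, yet no ulcer-related DUSS item can improve while a single ulcer stays open; the DFI score, already collected and analysed, should be the named measure

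*Protocol*

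**What the plan says.** Three places in the current protocol define clinical response, and all three use DUSS only.

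- The synopsis table of objectives and endpoints lists "Visual evaluation of the ulcer" as the clinical endpoint and gives the DUSS score as its variable.
- Section 14.2 states: "The measurement of this variable will be determined by the DUSS score at screening", and then repeats the score after Day 1, after Day 2, after the seven days of treatment, and at Day 15.
- Section 16.5 states: "The clinical response of Nu-3 via visual evaluation of the ulcer will be determined for each group". It scores DUSS at the same times and compares each dose with placebo by "An uncorrected chi-square analysis or a Fisher's Exact test". It does not say what change in DUSS counts as a response.

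Section 12.2 prints the two scoring tables. DUSS has four items scored 0 or 1: pedal pulses, probing to bone, location (toe or foot) and "Number of Ulcerations". The other table is the "Diabetic Foot Ulcer Wound Infection Score" (DFI). The Schedule of Events scores DFI at Visits 1, 4 and 5, but none of the three endpoint texts mentions it.

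On entry, 9.1.1 admits "Diabetic foot ulcer(s) with a DUSS Score of 0 to 3" and at most two ulcers. Section 9.1.2 excludes anyone whose ulcer probes to bone.

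SAP 8.1 lists change from baseline in DUSS, change from baseline in DFI, absence of each DFI component, and the Silhouette wound measurements. SAP 8.2 applies the same Wilcoxon rank sum test and the same two thresholds to DUSS and DFI change. It treats the ulcer measurements as additional endpoints but does not put DUSS above DFI or DFI above DUSS.

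**The concern.** An endpoint for clinical response should be able to move when the wound gets better. Purulence, redness, induration, pain and wound area could all resolve in an open ulcer while its DUSS stays the same. If so, a flat DUSS result does not separate a drug that does nothing from one that clears the infection without closing the ulcer in two weeks.

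Clinical response is a secondary objective, listed beside the choice of dose range for later studies. Under 14.2 and 16.5 the DUSS comparison is the clinical-response result. If DUSS shows nothing and DFI shows a difference, no stated rule says which of them answers the objective.

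**Working it through.** **Range of DUSS.** Four items scored 0 or 1 give 0 to 4, which matches the printed table. With probing to bone fixed at 0 on entry, the eligible range is 0 to 3. With a single ulcer the count item is also 0, so the range is 0 to 2.

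**What can improve, item by item.**

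| Item | One ulcer, still open | Two ulcers |
|---|---|---|
| Probing to bone | 0 at entry; can only worsen | 0 at entry; can only worsen |
| Location | fixed by site | taken as fixed (target ulcer) |
| Count | already 0 | falls by 1 only if one closes |
| Pedal pulses | may fall by 1; circulation, not wound | same |

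The largest improvement from ulcer-related items is therefore 0 points for one open ulcer, 0 for two open ulcers, and 1 if one of two closes. A subject who enters at DUSS 0, which 9.1.1 allows, cannot improve on any item. Location is held fixed because the Schedule of Events scores a target ulcer.

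**How many improvers a test would need.** Group sizes are 8 per dose (protocol 8.4). Pooled placebo is 5 × 2 = 10 under the protocol's five cohorts and 3 × 2 = 6 under the SAP's three. Suppose no placebo subject improves and every fall is 1 point.

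Protocol pairing, Fisher two-sided, a/8 v 0/10:
- a = 3: C(8,3)/C(18,3) = 56/816 = 0.069
- a = 4: C(8,4)/C(18,4) = 70/3060 = 0.023

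Fisher needs 4 of 8. Section 16.5 also allows the uncorrected chi-square, which would need 3 of 8: 18 × 30² / (8 × 10 × 3 × 15) = 4.5, p = 0.034.

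SAP pairing, exact two-sided test, a/8 v 0/6 (with every fall equal, the exact rank sum test gives the same values as Fisher):
- a = 4: [C(8,4) + C(6,4)]/C(14,4) = (70 + 15)/1001 = 0.085
- a = 5: [C(8,5) + C(6,5)]/C(14,5) = (56 + 6)/2002 = 0.031

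The exact test needs 5 of 8. SAP 8.2 does not say exact or asymptotic; the asymptotic version at 4 of 8 gives 0.048, or 0.058 with continuity correction.

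**How likely that is.** The documents do not give the share of subjects with two ulcers. As an assumption, take 10%, 20% or 30%, and suppose that every two-ulcer Nu-3 subject closes one ulcer and pulses do not change. From the binomial with n = 8:

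| Assumed share | P(at least 4 of 8) | P(at least 5 of 8) |
|---|---|---|
| 10% | 0.5% | 0.04% |
| 20% | 5.6% | 1.0% |
| 30% | 19% | 5.8% |

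These are ceilings for a dose that works as well as DUSS could show. The item-by-item result above needs no assumed share.

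**DFI for comparison.** Seven signs or symptoms: purulent discharge 0 or 3, nonpurulent drainage 0 or 1, and five items from 0 to 3. The maximum is 3 + 1 + 5 × 3 = 19. Any of the seven can improve while the ulcer remains open.

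**The case against.** The strongest reply is that DFI is not missing from the plan. Protocol section 16 commits to comparing every parameter with placebo and leaves detail to the SAP. The SAP then specifies DFI change and the DFI components, and Appendix A lists DUSS, DFI and ulcer tables for both ITT and PP. A reader might infer from 14.2 that the trial cannot detect clinical improvement, or that an awkward DFI result could be left out. The documents support neither inference.

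A second reply is that what remains is only a preference about ranking two secondary scores in a pilot whose primary objective is safety and which has no sample-size calculation. That limits the weight of the point but does not remove it. The protocol does choose between the scores, and it chooses the one that can hardly move. The two three-cohort protocol versions appended to the file gave the scores separate roles in their section 6.4.1: DFI improvement for clinical improvement of the wound, DUSS change for healing of a small ulceration. Those versions are superseded, so the difference is not itself an error, but it shows a split that current 14.2 and 16.5 lack.

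A third reply is that DFI has weaknesses too, and this stands. Sections 9.1.1 and 9.1.2 set no minimum DFI. Exclusion 8 removes subjects with fever and clinical features of active infection, which may lower entry scores further. Pain and tenderness make up 6 of the 19 points and may be blunted by neuropathy; section 6.2.2 of the appended versions says as much of burning at the ulcer site. DFI is also not scored at Visits 2 and 3, so it cannot supply the Day 1 and Day 2 readings in 14.2.

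**Conclusion.** The point holds in this form: the protocol's named measure of clinical response is insensitive by construction, and the SAP sets DFI beside it without saying which one answers the objective. For a subject with one ulcer that stays open, the possible gain on ulcer-related items is zero, and this follows from the scoring table and the entry criteria alone. The improver counts (4 of 8 against 10 placebo by Fisher, 5 of 8 against 6 by an exact test) assume no placebo improver; any probability of reaching them rests on an assumed share of two-ulcer subjects.

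It would go too far to say that DUSS can never fall, since the pulse item can change and one of two ulcers can close. The consequence is moderate: safety is primary and the DFI and wound analyses are already prespecified. It should be corrected because a null DUSS result would otherwise stand as the clinical-response finding. The differences between documents on Early Termination assessments, Silhouette at Visit 3 and imputation are separate matters and add nothing to this one.

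**What to change.** In the synopsis table, 14.2 and 16.5, name change from Visit 1 in the DFI Wound Infection Score at Visit 4 (end of MAD) as the clinical-response measure, with Day 15 as follow-up. For that measure, replace the chi-square or Fisher test in 16.5 with the SAP's Wilcoxon rank sum test against pooled placebo.

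In SAP 8.1 and 8.2, designate DFI change as the clinical-response endpoint, keep the ulcer measurements as additional, and report DUSS descriptively.

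Remove the Day 1 and Day 2 clinical-response readings from 14.2 and 16.5, or state that they are descriptive only.

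Report the baseline DFI distribution by dose group, including how many subjects enter at or near 0, so that a floor can be seen.

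The cost is low: edits to three protocol places and two SAP sections and one changed test, with no added visit or assessment. What is given up is a tested clinical reading before Visit 4, and the floor and neuropathy limits of DFI have to be accepted.

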### 15 PHARMACOKINETIC ASSESSMENT

There are no pharmacokinetic assessments being conducted in this study.

### 16 STATISTICAL CONSIDERATIONS

This study is designed to assess the safety and efficacy of Nu-3. Safety will be assessed by monitoring clinical laboratory parameters and treatment emergent adverse events. Efficacy will be assessed using endpoints of the clinical and microbiological response to Nu-3

Safety data including laboratory evaluations and vital signs assessments are summarized by dose group and time point of collection. Descriptive statistics are calculated for quantitative safety data, and frequency counts are compiled for classification of qualitative safety data. In addition, a mean change from baseline table is provided for vital signs and a shift table describing out of normal range shifts is provided for clinical laboratory results.

For all parameters, a comparison will be made of each active treatment group versus placebo using the appropriate statistical test. Unless otherwise indicated, all statistical tests will be

two-sided and differences will be considered statistically significant if the associated p-value is less than 0.05. All data will be presented in data listings.

A formal statistical analysis plan will be provided in a separate document. The Statistical Analysis Plan will contain additional details of the planned analysis along with tables, listings and figures that will become part of the Clinical Study Report. The Statistical Analysis Plan will be finalized prior to the database lock.

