#### **Statistical Analysis**

Summary tables (descriptive statistics and/or frequency tables) will be provided for all baseline variables, efficacy variables, and safety variables. Continuous variables will be described by descriptive statistics (n, mean, standard deviation, minimum, maximum, median, 95% confidence limits for the mean).

Frequency tables will be used to report adverse event frequency by system organ class (SOC), preferred term (PT), severity, and relationship to test article. All subjects receiving the test article will be included in the safety analyses.

Safety data including laboratory evaluations and vital signs assessments are summarized by dose group and time point of collection. Descriptive statistics are calculated for quantitative safety data, and frequency counts are compiled for classification of qualitative safety data. In addition, a mean change from baseline table is provided for vital signs and a shift table describing out of normal range shifts is provided for clinical laboratory results. Changes in physical examinations are described in the text of the final report.

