## 2. OBJECTIVES

The primary objective of the study is as follows:

- To assess the safety and tolerability of a twice daily, 7-day repeat topical doses of Nu-3 in adult male and female subjects with chronically infected diabetic ulcer.

The secondary objectives of the study are as follows:

- To assess the clinical and microbiological response to Bisphosphocin™ Nu-3.
- To support determination of the appropriate dose range of Nu-3 to be employed in future clinical studies.

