#### **4. GENERAL ANALYSIS CONSIDERATIONS**

The statistical analyses will be reported using summary tables and data listings. For all efficacy parameters, a comparison will be made of each active treatment group versus placebo using the appropriate statistical test. Unless otherwise indicated, all statistical tests will be two-sided and differences will be considered statistically significant if the associated p-value is less than 0.05. Continuous variables will be summarized with means, standard deviations (SD), medians, minimums, and maximums. Categorical variables will be summarized by counts and by percentage of subjects in corresponding categories. All data will be summarized by dose group (cohort), with all placebo subjects combined into one placebo arm.

Individual subject data obtained from the electronic data capture system, study lab, and any derived data will be presented by cohort for each subject in data listings.

The analyses described in this plan are considered *a priori*, in that they have been defined prior to database lock for individual subjects. Any analyses performed subsequent to database lock will be considered post-hoc and exploratory. Post-hoc analyses will be identified in the CSR.

All analyses and tabulations will be performed using SAS® Version 9.4 or higher on a Windows platform. Tables and listings will be presented in PDF format. Upon completion, all SAS® programs will be validated by an independent programmer. In addition, all program output will undergo a senior level statistical review. The validation process will be used to confirm that statistically valid methods have been implemented and that all data manipulations and calculations are accurate. Checks will be made to ensure accuracy, consistency with this plan, consistency within tables, and consistency between tables and corresponding data listings. Upon completion of validation and quality review procedures, all documentation will be collected and filed by the project statistician or designee.

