### **9.1 Adverse Events**

All AE summaries will be restricted to Treatment-Emergent Adverse Events (TEAE), which are

defined as those AEs that occurred after dosing and those pre-existing AEs that worsened during the study. Verbatim terms on case report forms will be mapped to preferred terms and system organ classes using the MedDRA dictionary (version 14.1).

Each AE summary will be displayed by dose group. Summaries that are displayed by system organ class and preferred terms will be ordered by descending order of incidence of system organ class and preferred term within each system organ class. Summaries of the following types will be presented:

- Subject incidence of TEAEs and total number of unique TEAEs by MedDRA system organ class and preferred term.
- Subject incidence of TEAEs by MedDRA system organ class, preferred term, and highest severity. At each level of subject summarization, a subject is classified according to the highest severity if the subject reported one or more events. An event with missing severity will not be imputed.
- Subject incidence of TEAEs by MedDRA system organ class, preferred term, and closest relationship to study drug (Not Related, Unlikely, Possibly, Probable, Definite). At each level of subject summarization, a subject is classified according to the closest relationship if the subject reported one or more events. AEs with a missing relationship will be considered definite related for this summary.
- Subject incidence of serious TEAEs and total number of unique serious TEAEs by MedDRA system organ class and preferred term.

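### The SAP limits the placebo comparison to efficacy where the protocol promises it for all parameters, leaving the primary safety endpoint with no estimated difference and no confidence interval

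*Protocol*

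**What the plan says.** Protocol section 16 first describes safety data in descriptive terms: summary statistics for measured variables, tallies for categorical ones, change tables for vital signs and shift tables for laboratory results. The next paragraph then says, without qualification, "For all parameters, a comparison will be made of each active treatment group versus placebo", using a suitable statistical test at a two-sided 0.05 level.

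SAP section 4 carries the same sentence with one added word: "For all efficacy parameters, a comparison will be made of each active treatment group versus placebo using the appropriate statistical test". It summarises categorical data by counts and percentages and combines all placebo subjects into one arm.

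The primary objective in SAP section 2 is "To assess the safety and tolerability of a twice daily, 7-day repeat topical doses of Nu-3", and the Study Design table in the protocol synopsis gives the primary endpoint as "Treatment emergent events related to clinical investigation product". For adverse events, SAP section 9.1 specifies "Subject incidence of TEAEs and total number of unique TEAEs by MedDRA system organ class and preferred term", with further breakdowns by highest severity, closest relationship and seriousness. It adds: "Each AE summary will be displayed by dose group". SAP section 8.2, by contrast, gives Fisher and Wilcoxon tests against pooled placebo for the efficacy endpoints.

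**The concern.** The two documents disagree on whether safety is compared with placebo, and the SAP does not mention the change. SAP section 1 promises that the study report will record deviations from the SAP. It does not cover the SAP's own departures from the protocol, so this one could go unreported.

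The narrowing falls on the primary objective: secondary efficacy endpoints receive formal contrasts and the primary safety endpoint receives none. The trial is also meant to support the dose range for later studies. A dose group with no related events, or one, in 8 subjects is compatible with a wide span of true rates, and a table of counts and percentages does not show that span. Nor does it show how uncertain any excess over placebo is, in a population where infected ulcers will produce background events.

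**Working it through.** **Text check**

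- Protocol section 16: comparison with placebo for all parameters, by test.
- SAP section 4: comparison for efficacy parameters only.
- SAP section 9: no test, difference or interval for any safety variable. Adverse events are subject incidence by dose group, vital signs are means, changes and outlier counts, and physical examinations are listed.
- SAP Appendix A: the titles of the safety tables indicate no contrast or interval. The shells in Appendix B are not in the text reviewed.

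**Inputs**

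- 8 Nu-3 and 2 placebo subjects per cohort (Protocol 8.4).
- Pooled placebo is 3 × 2 = 6 under the SAP's three cohorts (SAP 3), or 5 × 2 = 10 under the protocol's five (Protocol 8.3).
- Protocol 16.1 and SAP 10 state that no sample size was calculated, and neither document gives a safety event rate. There is therefore no plan figure to reproduce, and every event count and rate below is an assumption for illustration.

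**Exact (Clopper-Pearson) 95% limits for one group**

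For x events in n, the lower limit is the 0.025 quantile of Beta(x, n-x+1) and the upper limit is the 0.975 quantile of Beta(x+1, n-x). For x = 0 the upper limit reduces to 1 - 0.025^(1/n).

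- 0/8: upper limit 1 - 0.025^(1/8) = 1 - 0.631 = 36.9%
- 1/8: 0.3% to 52.7%
- 2/8: 3.2% to 65.1%
- placebo 0/6: upper limit 45.9%
- placebo 0/10: upper limit 30.8%

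**Difference from pooled placebo (Newcombe, from Wilson limits l and u)**

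Lower = d - √[(p1-l1)² + (u2-p2)²]; upper = d + √[(u1-p1)² + (p2-l2)²].

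For 2/8, p1 = 0.25, l1 = 0.0715 and u1 = 0.5907. For 0/6, p2 = l2 = 0 and u2 = 0.3903.

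- Lower: 0.25 - √(0.1785² + 0.3903²) = 0.25 - 0.429 = -0.179
- Upper: 0.25 + 0.3407 = 0.591
- 2/8 v 0/6 is therefore +25.0 points (-17.9 to +59.1).
- With 0/10 on placebo (u2 = 0.2775) it is +25.0 points (-8.0 to +59.1).
- 0/8 v 0/6 is 0 points (-39.0 to +32.4).

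**Chance of seeing an event at all**

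If the true rate is 10%, P(at least one in 8) = 1 - 0.9^8 = 0.57.

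**Would a test help?**

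- Against no placebo events, two-sided Fisher p < 0.05 first occurs at 5/8 v 0/6 (p = 0.031) or 4/8 v 0/10 (p = 0.023).
- Exact power for assumed true rates of 50% v 10% is 21% (8 v 6) or 37% (8 v 10).
- For 30% v 10% it is 3% or 9%.

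A p-value would almost always be uninformative; an interval would show what remains open.

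**The case against.** The best defence is that the SAP follows the protocol's specific safety text. The paragraph before the disputed sentence is descriptive, the synopsis calls for frequency tables for adverse events, and section 16 leaves details to the SAP. Descriptive safety reporting is normal in a pilot with no sample size calculation. This stands, and it is why the remedy is estimation rather than testing. It does not remove the conflict, because the protocol sentence is unqualified. Any reader could also compute the limits from the planned counts, so no data are lost; that makes the addition cheap rather than unnecessary.

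Three stronger readings are not supported:

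- A reader might infer that adverse events are not set against placebo at all. SAP section 4 pools placebo into one arm and section 9.1 displays each summary by dose group, so the rates stand side by side. What is missing is the estimated difference and its interval.
- A reader might take "95% confidence limits for the mean" in the synopsis as a promised interval for the primary endpoint. It applies to continuous variables; the endpoint is an incidence. SAP section 4 does omit those limits for continuous variables, but that is a separate, smaller mismatch.
- A reader might infer that dose escalation rests on reading 0/8 as safe. Escalation is governed by the dose-limiting toxicity (DLT) rule and committee review (Protocol 8.10), not by the final adverse event tables.

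**Conclusion.** The conflict between Protocol section 16 and SAP section 4 is real and unexplained, and it falls on the primary objective. In the SAP body text the primary safety endpoint has percentages by dose beside pooled placebo, but no estimated difference and no interval. A contrast in the unseen table shells cannot be ruled out.

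For scale, a clean dose group of 8 still allows a true rate up to 37%, and an observed 25-point excess over 0/6 on placebo is compatible with anything from -18 to +59 points. These figures rest on 8 evaluable subjects per dose, 6 placebo subjects and assumed event counts. The point is one of reporting and consistency. It does not show that the safety analysis is invalid or that safety should be tested.

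**What to change.** Before database lock:

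- **SAP 9.1.** For each dose group and pooled placebo, add overall rows for subjects with at least one TEAE and subjects with at least one TEAE judged at least possibly related, keeping the existing rule for missing relationship. Give each an exact (Clopper-Pearson) 95% interval and a risk difference from pooled placebo with a 95% interval. Label these descriptive, without p-values.
- **Protocol section 16.** Amend the sentence so that efficacy parameters are tested and safety parameters are estimated.
- **DLT.** A corresponding row can follow once the documents agree on grading. Protocol 8.10.5.2 defines DLTs by CTCAE version 3.0, while Protocol 13.4 grades adverse events by v4.02. These sections must be reconciled first, and the SAP would need to define the term.

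The cost is one protocol sentence, a short SAP insertion and a few table rows. The downside is that wide intervals will make the safety evidence look less favourable than percentages alone.
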